9.1.3 Outcome Categorization

The outcome of AEs must be recorded during the course of the study on the eCRF. Outcomes are as follows:

- Fatal
- Not Recovered/Not Resolved
- Recovered/Resolved
- Recovered/Resolved with Sequelae
- Recovering/Resolving
- Unknown

9.1.4 Symptoms of the Disease Under Study

Symptoms of the disease under study should not be classed as AEs as long as they are within the normal day-to-day fluctuation or expected progression of the disease. However, significant worsening of the symptoms should be recorded as an AE.

Adverse events should not be recorded in the eCRF if they are represented by any of the following:

Medical or surgical procedures (e.g., surgery, endoscopy, tooth extraction, transfusion); however, the condition that required the procedure is considered an adverse event if the situation developed or worsened after enrollment into the study.

Pre-existing diseases or baseline conditions present or detected at the start of the study that do not worsen.

Situations where an untoward medical occurrence has not taken place (e.g., hospitalization for elective surgery, social or convenience admissions).

9.1.5 Study-specific Events of Interest

Duration, course, and any medical intervention or dose adjustment will be captured in the eCRF. All study-specific events of interest should also be assessed for serious adverse event criteria and reported on the appropriate eCRF.

Hypotension

Since there is no single blood pressure measurement that will define hypotension for all study subjects, hypotension is to be recorded as an event of interest if the observed decrease in blood pressure was more than what the investigator anticipated.

In the conscious subject, whenever hypotension is recorded as an adverse event, it is to be classified as either a significant decrease in SBP **or** sufficiently low blood pressure defined as ≤ 80 mmHg.

Atrial Fibrillation

New-onset of persistent atrial fibrillation requiring intervention.

Other Clinically Significant Arrhythmias

Except for new-onset atrial fibrillation, clinically significant arrhythmias will be defined as any rhythm that requires medical intervention such as pacing, or the addition, removal, or dose adjustment of any drugs in an attempt to treat the abnormal rhythm.

Aborted Resuscitated Death

The incidence of survival following a cardiac arrest.

Stroke

Stroke will be defined as a new the rapid onset of a new neurological deficit of cerebrovascular cause that persists beyond 24 hours (non-fatal) or is interrupted by death within 24 hours (any) with evidence of new neurological lesion on imaging modalities.

Ongoing Adverse Event Collection

During ongoing study and routine standard of care visits, the patient should be asked if they have experienced any of the following changes:

- Palpitations associated with:
 - Shortness of breath
 - Significant lightheadedness
 - Passing out/syncope
- Edema (swelling):

- Frequency (never, occasionally, constantly)
- Shortness of breath with activity:
 - Frequency (rarely, often, constantly)
- Diuretic use:
 - Changes (increase, no change, decrease)
- Hospitalization or Emergency Room visits

All changes to a patient's health status, including AEs, concomitant medication/procedures, and hospitalizations (including ER visits) must be documented in the case report form.

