1.3.6 Levosimendan Clinical Safety

The primary safety events of interest in levosimendan administration are hypotension and tachycardia.

In integrated safety data in heart failure subjects from placebo-controlled IV levosimendan studies, there are no differences in the frequencies of decreased BP in levosimendan treated subjects compared to placebo-treated subjects (23.1% vs. 23.1%). However, in the largest placebo-controlled trial with IV levosimendan (REVIVE II) a statistically significantly greater proportion of levosimendan-treated subjects experienced decrease in BP (52.6%) compared to the placebo group (37.9%), $p < 0.001$. This study employed a high bolus dose, then titration after 1 hour to $0.2 \mu\text{g/kg/min}$ for 23 hours.

In the integrated data of placebo-controlled IV levosimendan studies, atrial tachycardia and fibrillation are seen in 8.2% in the levosimendan group compared to 5.4% in the placebo group ($p = 0.024$). This difference was also seen in REVIVE II (9% vs. 2%, $p < 0.001$). In REVIVE II, a statistically significant difference in the incidences of ventricular tachycardia could also be seen (25% in the levosimendan group and 17% in the placebo group, $p = 0.031$). However, in the integrated data, the events in the grouping of 'ventricular tachycardia and fibrillation' are reported in 10.0% of the levosimendan treated subjects and in 11.3% of the placebo subjects ($p = 0.371$).

The incidences of worsening heart failure (15.6% vs. 28.4%, $p < 0.001$) and renal function disturbances (6.9% vs. 10.4%, $p = 0.007$) are significantly lower in the levosimendan group than in the placebo group.

No statistically significant difference in cardiac ischemia (7.3% vs. 8.9%, $p = 0.233$), decreased hemoglobin (2.3% vs. 3.8%, $p = 0.058$), decreased potassium (4.9% vs. 7.0%, $p = 0.059$) or increased blood glucose (1.6% vs. 2.6%, $p = 0.117$) are seen between levosimendan and placebo groups. It is noteworthy that although no statistically significant differences in the frequency of decreased hemoglobin and decreased potassium are seen, the numerical differences favor levosimendan. This is in contrast to the laboratory safety variable analyses; in IV studies decreases in hemoglobin and serum potassium have been consistently reported ([29](#), [47](#)).

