14.3 ATTACHMENT 3: Cardiac Event Recommendations and Management

Changes in BP or HR that could represent a significant safety concern should be reported to the treating physician.

If the subject meets any of the dose-limiting event criteria, the following actions on study drug should be undertaken:

1. Blood pressure (systolic) management
 - a. Minimum allowed BP 100 mmHg systolic
 - i. If <120 on antihypertensive meds, recommend reduce or discontinue
 - ii. If >120 on antihypertensive meds, no change.
2. Low blood pressure (systolic <100) management **without symptoms**
 - a. On diuretics
 - i. With edema = no change
 - ii. No edema = reduce or withdraw
 - b. On antihypertensive meds
 - i. Reduce/withdraw
 - c. On no diuretics or antihypertensive meds
 - i. No symptoms = observe
 - ii. BP <90 = reduce levosimendan dose
3. **Symptomatic** low BP management
 - a. Follow recommendations of asymptomatic scenario (above), **and**
 - i. BP <100 mild symptoms = levosimendan dose reduction
 - ii. BP <100 severe symptoms = IV phenylephrine and levosimendan dose reduction
 - iii. BP <90 on lowest dose = discontinue study
4. Sinus tachycardia at rest
 - a. HR >110 = repeat three times per protocol and obtain BP to validate
 - b. HR >110 without symptoms = in the absence of hypotension (above), observe
 - c. HR >110 with symptoms of worsening dyspnea in the absence of hypotension (above) = levosimendan dose reduction
 - d. HR >120 (validated) without symptoms = obtain ECG to determine if sinus tachycardia or atrial-fibrillation. *(If HR > 120, the treating physician should be contacted.)*
 - i. If sinus tachycardia = levosimendan dose reduction or withdraw
 - ii. If atrial fibrillation = heart rate drug management
 - e. Persistent HR >120 despite any/all above measures = discontinue study

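### Recording of hypotension and tachycardia, the drug's two named main risks, turns on what each investigator expected, so the same finding may be captured inconsistently

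*Protocol*

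**What the plan says.** Protocol section 1.3.6 states the priority: "The primary safety events of interest in levosimendan administration are hypotension and tachycardia".

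Protocol section 9.1.5 sets the event-of-interest rules. It first gives a reason for having no cut-off, namely that no one pressure reading suits every subject. It then says that "hypotension is to be recorded as an event of interest if the observed decrease in blood pressure was more than what the investigator anticipated". Once hypotension has been recorded as an adverse event in a conscious subject, "it is to be classified as either a significant decrease in SBP", which carries no number, or as "sufficiently low blood pressure defined as ≤ 80 mmHg". The other entries are new-onset persistent atrial fibrillation, other clinically significant arrhythmias (rhythms needing intervention, including a drug dose change made to treat the rhythm), resuscitated arrest and stroke. There is no entry for tachycardia or raised heart rate. For events of interest, the eCRF is to hold duration, course, intervention and dose adjustment.

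Protocol section 8.1.2.4 makes a vital-sign deviation an adverse event only when the investigator considers it clinically significant.

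Attachment 3 uses fixed levels: "Minimum allowed BP 100 mmHg systolic"; "BP <100 mild symptoms = levosimendan dose reduction"; "BP <90 = reduce levosimendan dose" (no symptoms, on neither diuretics nor antihypertensives); and, within the symptomatic branch, "BP <90 on lowest dose = discontinue study". For heart rate it acts on levosimendan above 110 bpm with worsening dyspnea and above 120 bpm in validated sinus tachycardia.

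**The concern.** This is an open-label, single-arm study whose primary objective is safety and tolerability. Its main result is a set of adverse-event and vital-sign counts, with no control group to absorb differences in recording habits.

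Levosimendan is a known vasodilator, and the protocol tells investigators what to expect. Section 1.3.4 reports a heart-rate rise of 7-8 bpm on oral drug and no change on placebo. In the oral heart-failure studies in section 1.3.6, increased heart rate was reported in 7.6% against 1.7% on placebo, palpitations in 6.5% against 0.6%, and hypotension in 6.0% against 3.4%; tachycardia as a term was similar (6.5% against 6.8%). A trigger that depends on a fall exceeding expectation is weakest for effects the investigator already expects.

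At stake are whether two sites treat the same finding alike, and whether the added detail on course and dose change is kept for the events that matter most.

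**Working it through.** No power, alpha or sample-size figure bears on this point, since the SAP plans no hypothesis test. The check sets the rules side by side.

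**Step 1. What triggers a drug action, and what triggers recording**

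| Finding | Attachment 3 action on levosimendan | Event of interest under 9.1.5 |
|---|---|---|
| SBP <100, symptomatic | Dose reduction | Only if the fall exceeded expectation |
| SBP <90, no symptoms, on neither diuretics nor antihypertensives | Dose reduction | Only if the fall exceeded expectation |
| SBP <90 on lowest dose (symptomatic branch) | Study discontinuation | Only if the fall exceeded expectation |
| HR >110 with worsening dyspnea, no hypotension | Dose reduction | No named entry; arguably an arrhythmia whose treatment includes a dose change |
| HR >120, validated sinus tachycardia | Reduction or withdrawal | As in the row above |
| HR >110, no symptoms, no hypotension | Observe | None |

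**Step 2. The 80 mmHg figure.** It is the only number in the hypotension entry and lies 90 − 80 = 10 mmHg and 100 − 80 = 20 mmHg below the two Attachment 3 levels. It does not decide whether a case is recorded. It is one of two classes for hypotension already entered as an adverse event, and a case at 85 mmHg can go into the other class. What is missing is any statement of how that class, which has no number, relates to the Attachment 3 levels.

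**Step 3. A worked case.** Take an asymptomatic patient, on neither diuretics nor antihypertensives, with SBP 85 mmHg and a resulting dose reduction. An investigator who expected the fall need not flag it and, if it is judged not clinically significant, need not enter an adverse event under section 8.1.2.4. Another investigator, surprised by the same reading, flags it and enters one. Both can point to protocol text. The treatment-emergent adverse event (TEAE) tables would show 0 in one case and 1 in the other.

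**Step 4. Do the planned outputs recover the difference?**
- SAP section 3.5.1 counts all TEAEs by system organ class and preferred term, with categories for those leading to drug or study discontinuation. It has no category for dose reduction and no event-of-interest table.
- SAP section 3.4.1 makes the incidence of abnormal blood pressure and pulse rate a primary endpoint without defining abnormal. Section 3.5.3 provides listings only, and the list of tables has no vital-sign table, although Protocol section 10.8 says vital signs will be summarized by treatment group and visit.
- Readings between visits are in the diary, but the SAP has no diary listing. Weeks 2 and 4 may be remote, and visits become yearly after Week 48. An out-of-clinic finding may reach the results only through a discretionary adverse event.

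**Step 5. Weight of one patient.** Protocol section 1.3.5 gives 37 randomised in the parent study. If that is the only source of patients, this study has at most 37, and one patient is at least 1/37 = 2.7 percentage points. This is the weight of one case and does not estimate missed cases.

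**The case against.** The strongest reply is that the event-of-interest flag and adverse-event recording are separate, and most of that reply stands. Protocol section 9.1 collects all adverse events with no exemption for expected effects, and section 9.1.5 requires every change in health status to be documented in the case report form. A reader might infer that an anticipated fall goes unrecorded altogether. The documents do not say so: it is only not recorded as an event of interest. A reader might also infer that the flag biases the primary endpoint, but no SAP table uses the flag.

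A second tempting reading treats 80 mmHg as the recording threshold, so that everyone reduced or withdrawn between 80 and 100 mmHg is lost. Step 2 shows otherwise. The discontinuation rule at <90 also applies to symptomatic patients, and section 3.4.1 requires an adverse event that is a reason for stopping to be recorded as such. The asymptomatic reduction at <90 may reach few patients, because section 4.2 calls for optimal diuretic management as indicated.

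On tachycardia, a levosimendan reduction for sinus tachycardia can reasonably be placed under the arrhythmia entry. Raised heart rate that is only observed cannot.

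Finally, reliance on judgement is deliberate and explained in section 9.1.5. The explanation is weakened because Attachment 3 applies fixed levels across subjects. What remains is that the fallback in section 8.1.2.4 is investigator opinion too, so nothing in the chain is objective.

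**Conclusion.** The point holds as a risk of inconsistent recording. Hypotension and tachycardia are the protocol's own first-named risks. One has a trigger based on expectation, the other has no entry, and the general vital-sign rule also depends on opinion. Findings that lead to an Attachment 3 action on levosimendan may be recorded differently between investigators, could be under-counted as adverse events, and may lose the detail on duration, course and dose adjustment. If there is a shift, expected drug effects are the ones more likely to go unflagged.

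The documents do not support the stronger statement that these events are under-counted. All adverse events are collected, all TEAEs are tabulated, and no planned count uses the flag. The size cannot be computed, because no blood pressure or heart rate distribution is given for this study. The 2.7-point weight per patient assumes that TNX-LVO-04 is the only parent study.

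The 80 mmHg class and the Attachment 3 levels need reconciling. No view is taken here on which clinical level is right.

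**What to change.** 1. In Protocol section 9.1.5, replace the condition about exceeding expectation with a recording rule. Any blood pressure or heart rate finding that leads to an Attachment 3 action on levosimendan (reduction, interruption, withdrawal or study discontinuation) is recorded as an adverse event of interest, with the measured value and the dose at the time.
2. List tachycardia in section 9.1.5 on the same basis.
3. State how the 80 mmHg class and the class without a number relate to the Attachment 3 levels.
4. Add one SAP table, by IV and oral period, of these events and of visit SBP and heart rate values beyond the levels already in Attachment 3 (SBP <100 and <90; HR >110 and >120). The second part also covers raised heart rate that is only observed, which the recording rule alone would miss.

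The cost is one paragraph of protocol text, an eCRF completion note and one table. If recording can no longer be changed, the visit-value part of the table can still be produced from data already collected, though it will not see readings between visits. The downside is a somewhat higher reported rate of hypotension and tachycardia. No Attachment 3 action or threshold changes.

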9.1.6 Clinical Laboratory Evaluations

A change in the value of a clinical laboratory investigation can represent an AE if the change is clinically relevant or if, during treatment with the investigational product, a shift of a parameter is observed from a normal value to an abnormal value, or a further worsening of an already abnormal value. When evaluating such changes, the extent of deviation from the reference range, the duration until return to the reference range, either while continuing treatment or after the end of treatment with the investigational product, and the range of variation of the respective parameter within its reference range, must be taken into consideration.

If, at the end of the treatment phase, there are abnormal clinical laboratory values which were not present at baseline, further clinical or laboratory investigations should be performed until the values return to within the reference range or until a plausible explanation (e.g., concomitant disease) is found for the abnormal clinical laboratory values.

The Investigator should decide, based on the above criteria and the clinical condition of a subject, whether a change in a clinical laboratory parameter is clinically significant and therefore represents an AE.

9.1.7 Pregnancy

All pregnancies are to be reported from the time first exposure to study drug until the subject discontinues the study.

Any report of pregnancy for any female study participant must be reported within 24 hours to the Medpace Pharmacovigilance Department using the Medpace Pregnancy Report Form.

The female study participant must be withdrawn from the study.

Every effort should be made to gather information regarding the pregnancy outcome and condition of the infant. It is the responsibility of the Investigator to obtain this information

within 30 calendar days after the initial notification and approximately 30 calendar days postpartum.

Pregnancy complications such as spontaneous abortion/miscarriage or congenital abnormality are considered SAEs and must be reported using the provided SAE form. Note: An elective abortion is not considered an SAE.

In addition to the above, if the Investigator determines that the pregnancy meets serious criteria, it must be reported as an SAE using the provided SAE form as well as the Pregnancy Report Form. The test date of the first positive serum/urine HCG test or ultrasound result will determine the pregnancy onset date.

In animal studies, levosimendan was not teratogenic, but it caused a generalized reduction in the degree of ossification in rat and rabbit fetuses with anomalous development of the supraoccipital bone in the rabbit. When administered before and during early pregnancy, levosimendan reduced fertility (decreased the number of corpora lutea and implantations) and exhibited developmental toxicity (decreased pups per litter and increased the number of early resorptions and post-implantation losses) in the female rat. The effects were seen at clinical exposure levels.

9.1.8 Abuse, Misuse, Overdose, and Medication Error

Abuse, misuse, overdose, or medication error (as defined below) must be reported to the Sponsor according to the SAE reporting procedure whether or not they result in an AE/SAE as described in Section 9.2. Note: The 24 hour reporting requirement for SAEs does not apply to reports of abuse, misuse, overdose, or medication errors unless these result in an SAE.

The categories below are not mutually exclusive; the event can meet more than 1 category.

- **Abuse** – Persistent or sporadic intentional intake of investigational product when used for a non-medical purpose (e.g., to alter one's state of consciousness or get high) in a manner that may be detrimental to the individual and/or society.
- **Misuse** – Intentional use of investigational product other than as directed or indicated at any dose (Note: this includes a situation where the investigational product is not used as directed at the dose prescribed by the protocol).
- **Overdose** – Intentional or unintentional intake of a dose of an investigational product exceeding a prespecified total daily dose
- **Medication Error** – An error made in prescribing, dispensing, administration, and/or use of an investigational product. Medication errors are reportable to the Sponsor as defined below.

Cases of subjects missing doses of product are not considered reportable as medication errors.

Medication errors should be collected/reported.

The administration and/or use of an expired product should be considered as a reportable medication error.

9.2 Serious Adverse Event Procedures

9.2.1 Reference Safety Information

The reference for safety information for this study is the Investigator's Brochure/Summary of Product Characteristics/SmPC which the Sponsor has provided to all Investigators.

9.2.2 Reporting Procedures

Initial Reports

All SAEs must be reported to Medpace Clinical Safety **within 24 hours** of the knowledge of the occurrence.

To report the SAE, complete the SAE form electronically in the electronic data capture (EDC) system for the study. When the form is completed, Medpace Safety personnel will be notified electronically by the EDC system and will retrieve the form. If the event meets serious criteria and it is not possible to access the EDC system, send an email to Medpace Safety or call the Medpace SAE hotline (phone number listed below), and fax/email the completed paper SAE form to Medpace (contact information listed below) within 24 hours of awareness. When the EDC system becomes available, the SAE information must be entered within 24 hours of the system becoming available.

Follow-Up Reports

The investigator must continue to follow the subject until the SAE has subsided or until the condition becomes chronic in nature, stabilizes (in the case of persistent impairment) or the subject dies.

Within 24 hours of receipt of follow-up information, the investigator must update the SAE form electronically in the EDC system for the study and submit any supporting documentation (e.g., subject discharge summary or autopsy reports) to Medpace Clinical Safety via fax or e-mail. If it is not possible to access the EDC system, refer to the procedures outlined above for initial reporting of SAEs.

Safety Contact Information:
Medpace Clinical Safety

Medpace SAE hotline – USA:
[contact], dial “3” **or** [contact], dial “3”

[contact] **or** [contact]
E-mail: [contact]

Note: The 24-hour reporting requirement for SAEs does not apply to reports of abuse, misuse, overdose, or medication errors unless they result in an SAE.

9.2.3 Serious Adverse Event Definition

A Serious Adverse Event (SAE) is any untoward medical occurrence (whether considered to be related to investigational product or not) that at any dose:

- Results in death
- Is life-threatening

NOTE: The term ‘life-threatening’ in the definition of ‘serious’ refers to an event in which the subject was at risk of death at the time of the event; it does not refer to an event which hypothetically might have caused death if it was more severe.
- Requires hospitalization or prolongation of existing hospitalization
- Results in persistent or significant disability/incapacity
- Is a congenital abnormality/birth defect
- Is an important medical event; Note: Important medical events that may not result in death, be life-threatening, or require hospitalization may be considered an SAE when, based upon appropriate medical judgment, they may jeopardize the subject and may require medical or surgical intervention to prevent 1 of the outcomes listed in this definition. Examples of such medical events include allergic bronchospasm requiring intensive treatment in an emergency room or at home; blood dyscrasias or convulsions that do not result in subject hospitalization; or the development of drug dependency or drug abuse.

Hospitalizations, which are the result of elective or previously scheduled surgery for pre-existing conditions, which have not worsened after initiation of treatment, should not be classified as SAEs. For example, an admission for a previously scheduled ventral hernia repair would not be classified as an SAE.

However, complication(s) resulting from a hospitalization for an elective or previously scheduled surgery that meets serious criteria must be reported as SAE(s).

